7.1 COVID-19 Impact

No changes to the planned analysis of the efficacy or safety endpoints are planned due to the impact of Coronavirus disease 2019 (COVID-19) outbreak.

The following sensitivity analyses based on IRC assessment will be performed on participants in the combination arm from the mFAS:

- Best Overall Response (BOR) and related endpoints will be analyzed as described in Sections 14.1.1, 14.2.2 and 14.2.4 but considering only participants with no study treatment discontinuation due to COVID-19.
- Progression Free Survival (PFS) will be analyzed as described in Section 14.2.5; however, participants who discontinued study treatment due to COVID-19 and subsequently had an event (PD or death) will be censored at the date of the event.

Additional outputs (summary table and listing) will be generated for a description of the impact by COVID-19 on the study. The number and percentage of participants will be presented for the following findings due to COVID-19:

- Potentially affected by COVID-19
- Adverse Events
- Protocol deviations (important and non-important)
- Missed Visits (including number of missed visits)
- Missed efficacy evaluations (including number of missed efficacy evaluations)
- Tele-visits (remote audio video or telephone call) or emails replacing site visits (including number of tele-visits/emails)
- Drug administration missed doses (of osimertinib and/or tepotinib)
- Drug administration dose adjustments (of osimertinib and/or tepotinib)
- Laboratory testing performed by external laboratory unit
- Treatment discontinuation (of osimertinib and/or tepotinib)
- End of tumor assessment visits
- Study discontinuation
- Death

Potentially affected participants (either due to infection or due to circumstances of social distancing affecting the capabilities of sites/hospitals etc.) are defined as:

- a) Patients who started treatment after start of the COVID-19 pandemic, or
- b) Patients who started treatment prior to start of the COVID-19 pandemic and were still ongoing in the study after the start of the pandemic (i.e., neither died or withdrew from study prior to start of the pandemic).

The start of COVID-19 pandemic will be defined by country as the earliest date of either the date of the first death from COVID-19 occurred in each country according to the published data by European Centre for Disease Prevention and Control on 26th June 2020 (https://www.ecdc.europa.eu/en/publications-data/download-todays-data-geographic-distribution-covid-19-cases-worldwide) or 11th March 2020 (when the WHO declared COVID-19 pandemic).

A frequency table will be produced for the SAF analysis set to present the number of participants with important protocol deviations related to COVID-19 (categorized by frequency of participants with an important protocol deviation overall as well as by category of protocol deviation and type of protocol deviation). A separate table for the non-important protocol deviations related to COVID-19 (categorized by frequency of participants with a non-important protocol deviation overall as well as by category of protocol deviation overall as well as by categorized by frequency of participants with a non-important protocol deviation overall as well as by category of protocol deviation overall as well as by category of protocol deviation) will also be produced.

A frequency table based on concomitant medication data will be produced for the SAF analysis set to present the number of participants with COVID-19 vaccinations. COVID-19 vaccinations will be identified according to the Standardized Drug Groupings (SDGs) subgroup "Vaccines for COVID-19" and corresponding SDG subcategories of the latest version of the WHO-DD. The summary will include counts for vaccines that were given prior to first administration of any study treatment as well as concomitant vaccines.

In addition, separate listings of COVID-19 related adverse events, vaccinations and protocol deviations will also be produced.

Outputs related to disposition and exposure will be amended to present reason of treatment/study discontinuations due to COVID-19 and treatment delays due to COVID-19 (if possible).

Laboratory results performed by external laboratory units will be included in the summary statistics and shift analyses, provided that normal ranges are not missing; if they are missing, results will be listed and included in summary statistics outputs only.

8 Analysis Populations and Subgroups

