	Supplementary Analyses: as supplementary analyses of the primary estimand but with the endpoint of the main estimand				
Duration of Response	Endpoint: Duration of response according to RECIST 1.1 as assessed by IRC, measured by time from first documentation of objective response to PD or death, occurring within 126 days after last evaluable tumor assessment or first study intervention				
	Population: Patients with MET amplification determined centrally by FISH (T+), with advanced or metastatic NSCLC harboring activating EGFR mutations and having acquired resistance to prior first-line osimertinib therapy with objective response according to RECIST 1.1				
	Treatment: as primary estimand				
	Intercurrent Event Strategy:				
	 Death within 126 days after last evaluable assessment: the intercurrent event will be considered as event of interest (composite strategy) 				
	• Discontinuation of treatment: ignoring the intercurrent event (treatment-policy strategy)				
	• Start of subsequent anticancer treatment: ignoring the intercurrent event (treatment-policy strategy)				
	Population Level Summary:				
	 Median duration of response based on Kaplan-Meier estimates and 95% 2-sided CI 				
	• Kaplan-Meier estimates, including the Kaplan-Meier estimate at 6 months				
	Rate of participants by response duration categories				
	Sensitivity Analyses:				
	As main estimand, but using Investigator assessment instead of IRC assessment				
	Supplementary Analyses:				
	• As main estimand and sensitivity analysis, but based on different populations: L+, T+ and/or L+.				
	• As main estimand and sensitivity analysis, but for tepotinib monotherapy as, to be repeated also on populations L+, T+ and/or L+.				
PFS	Endpoint: Progression-free survival measured by time from first study intervention to PD according to RECIST 1.1 (by IRC) or death, occurring within 126 days after last evaluable assessment or first study intervention				
	Population: as primary estimand				
	Treatment: as primary estimand				
	Intercurrent Event Strategy:				
	• Death within 126 days after last evaluable assessment or first study intervention: the intercurrent event will be considered as event of interest (composite strategy)				
	• Discontinuation of treatment: ignoring the intercurrent event (treatment-policy strategy)				

Endpoint	Estimand Attributes			
	• Start of subsequent anticancer treatment: ignoring the intercurrent event (treatment-policy strategy)			

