	 Population Level Summary: Median PFS time based on Kaplan-Meier estimates and 95% 2-sided CI Kaplan-Meier estimates 			
	 Sensitivity Analyses: As main estimand, but using Investigator assessment instead of IRC assessment. As main estimand but censoring participants who discontinued treatment due to COVID-19 before occurrence of an event at the time of event. 			
	 Supplementary Analyses: As main estimand and sensitivity analysis, but based on different populations: L+, T+ and/or L+. As main estimand, but considering the start of subsequent anti-cancer therapy as PD (composite strategy), to be repeated also on populations L+, T+ and/or L+. As main estimand and sensitivity analysis, based on tepotinib monotherapy as treatment., to be performed also on populations L+, T+ and/or L+. 			
OS	Endpoint: OS as measured by time from first study intervention to death			
	Population : as primary estimand			
	Treatment: Tepotinib combined with osimertinib, taking subsequent anti-cancer therapy int account			
 Intercurrent Event Strategy: Discontinuation of treatment: ignoring the intercurrent event (treatment-policy strat Start of subsequent anticancer treatment: ignoring the intercurrent event (treatment-strategy) 				
	 Population Level Summary: Median OS time based on Kaplan-Meier estimates and 95% 2-sided CI Kaplan-Meier estimates 			
	 Supplementary Analyses: As main estimand and sensitivity analysis, but based on different populations: L+, T+ and/or L+ 			
HRQoL	Endpoint: Change from baseline in health state as measured by the Visual Analogue Scale (VAS) as a component of the EQ-5D-5L questionnaire; global health status, sub-dimensions of functional scales and symptoms scales as measured by EORTC QLQ-C30; cough, chest pain, dyspnea, fatigue, appetitive and overall severity of symptoms measured by NSCLC-SAQ.			
	Population: as primary estimand			

Endpoint	Estimand Attributes			
	Treatment: as primary estimand			
	 Intercurrent Event Strategy: Discontinuation of treatment: ignoring the intercurrent event (treatment-policy strategy) Start of subsequent anticancer treatment: ignoring the intercurrent event (treatment-policy strategy) 			
	 Population Level Summary: LS Mean changes from baseline analysis for cough, pain and dyspnea (NSCLC-SAQ) General descriptive statistics to summarize values and change from baseline by visit 			

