14.2.5 Progression Free Survival by IRC and by Investigator

PFS time is defined as the time (in months) from first administration of study treatment to the date of the first documentation of PD or death due to any cause within 126 days of the last tumor assessment, whichever occurs first (i.e., date of PD/death - date of last evaluable tumor assessment \leq 126).

PFS data will be censored on the date of the last evaluable tumor assessment for participants who do not have an event (PD or death) or for participants with an event more than 126 days after the last tumor assessment (i.e. date of PD/death - date of last evaluable tumor assessment > 126).

The last evaluable tumor assessment is defined as the last tumor assessment result that is not "NE".

Participants who do not have an evaluable post-baseline tumor assessment will be censored at the date of the start of study treatment unless death occurred within 126 days of the first dose of study treatment in which case the death will be considered an event.

If a participant has only not evaluable tumor assessments prior to a PD which is within 126 days of the first dose of study treatment, the PD will be considered an event; if the PD is after the 126 days, the PFS will be censored at the date of first dose.

The censoring and event date options to be considered for the PFS are presented in Table 6.

Table 6. Date of event / censoring definition for PFS analysis

Status		Censoring	Date of event / censoring
Progressed or died	Within 126 days after last response assessment of CR, PR or SD or start of treatment	Event	Minimum (Date of PD, Date of death)
	Otherwise	Censored	Date of last tumor assessment with outcome CR, PR or SD or date of the start of treatment, whatever is later
Neither progress	sed nor died	Censored	Date of last tumor assessment with outcome CR, PR or SD or date of the start of treatment, whatever is later

60/94

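### The COVID-19 sensitivity analysis of PFS censors participants at their own progression or death, so it can only match or raise the main PFS curve

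*SAP*

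**What the plan says.** SAP 7.1 introduces its COVID-19 analyses with "The following sensitivity analyses based on IRC assessment will be performed on participants in the combination arm from the mFAS". For PFS it refers to Section 14.2.5 and then makes an exception: participants "who discontinued study treatment due to COVID-19 and subsequently had an event (PD or death) will be censored at the date of the event". The PFS row of the estimands table in SAP 14 gives the same rule: "As main estimand but censoring participants who discontinued treatment due to COVID-19 before occurrence of an event at the time of event". The parenthesis in 7.1 defines the event as PD or death, so the date meant cannot be the date of COVID-19 discontinuation.

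Three other places matter.

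- The main PFS estimand (SAP 14) handles treatment discontinuation by treatment policy, so later PD or death counts.
- The main censoring convention is in SAP 14.2.5: "PFS data will be censored on the date of the last evaluable tumor assessment" when there is no event, or when the event comes more than 126 days after that assessment. Table 6 states the censoring date as "Date of last tumor assessment with outcome CR, PR or SD or date of the start of treatment, whatever is later". It never uses a PD or death date.
- The parallel COVID-19 analysis of best overall response in SAP 7.1 leaves the COVID-19 discontinuers out altogether.

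No intercurrent-event strategy is named for the COVID-19 version of PFS.

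**The concern.** Kaplan-Meier needs censoring that carries no information about the event time. Here the censoring time is the event time: a COVID-19 discontinuer is counted as progression-free and at risk up to PD or death, then leaves without an event. The result is not treatment-policy PFS, because real events are dropped. It is not PFS had COVID-19 discontinuation not occurred, because follow-up after discontinuation stays in the risk set. It is not PFS among non-discontinuers either.

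A sensitivity analysis should be able to show that a result is fragile. This one cannot return a lower PFS than the main analysis, so agreement between the two would give false reassurance. The rule can take effect in practice: Protocol 4.1 and 8.1 continue tumor assessments after treatment stops for reasons other than PD or death, so later events will be recorded and then relabelled.

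**Working it through.** **Inputs.** The rule comes from SAP 7.1 and SAP 14, and the estimator (Kaplan-Meier) from SAP 14.2.5. The scan schedule, every 6 weeks to 9 months and then every 12 weeks, is in Protocol 8.1. The planned 80 participants in the primary analysis set are in Protocol 9.2. The plan has no figure of its own to reproduce. *Assumed:* exponential PFS with median 6 months (range 4 to 12), and 2% to 10% discontinuing due to COVID-19 before their event.

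**1. Direction.** S(t) = Π(1 − d_j/n_j). The rule leaves n_j unchanged and lowers d_j on the discontinuers' event dates, so every factor is at or above its main-analysis value. If an event falls more than 126 days after the last assessment, the main analysis censors at that assessment. Moving the censoring to the later event date enlarges risk sets, which again can only raise the curve. Numerical check: the sensitivity curve was below the main curve in 0 of 20,000 random small data sets and 0 of 36,000 simulated trials of 80.

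**2. Small example.** Ten participants have events at months 1 to 10; those at months 3 and 6 are COVID-19 discontinuers. Main S(6) = 4/10 = 0.40. Under the SAP rule S(6) = 9/10 × 8/9 × 6/7 × 5/6 = 0.571. If all ten were discontinuers, the curve would stay at 1.0 although all ten had events.

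**3. Size, closed form, non-informative discontinuation.** Event hazard L = ln2/6 = 0.1155 per month. If a proportion p discontinues before the event, the discontinuation hazard is M = Lp/(1−p). Of those at risk at time t, a fraction exp(−Mt) has not discontinued, so the counted hazard is L·exp(−Mt). The curve converges to exp{−[(1−p)/p]·[1 − exp(−Mt)]}, with median −ln(1 − p·ln2/(1−p))/M.

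| p | M | Cumulative counted hazard, month 12 | 12-month PFS | Median (months) |
|---|---|---|---|---|
| truth | – | 1.3863 | 25.0% | 6.00 |
| 2% | 0.00236 | 49 × 0.02790 = 1.3669 | 25.5% | 6.04 |
| 5% | 0.00608 | 19 × 0.07036 = 1.3369 | 26.3% | 6.11 |
| 10% | 0.01284 | 9 × 0.14276 = 1.2848 | 27.7% | 6.24 |

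Censoring at discontinuation leaves the hazard at L and returns 25.0%. For assumed medians of 4 to 12 months, the 12-month excess under the SAP rule is 0.6 to 1.5 points at 5% and 1.3 to 3.1 points at 10%.

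**4. On the protocol scan schedule.** One million simulated participants, PD dated at the next scan, 20% of events assumed to be deaths, cut-off assumed uniform over 9 to 24 months. 12-month PFS in the same data:

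| p | Main | SAP rule | Censor at last assessment on or before discontinuation |
|---|---|---|---|
| 5% | 27.0% | 28.5% | 27.0% |
| 10% | 27.0% | 30.1% | 26.9% |

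Repeat runs agreed to within about 0.3 points.

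**5. At n = 80.** Relabelling 1, 2 or 4 randomly chosen events raised 12-month PFS by 0.5, 1.1 or 2.1 points on average and never lowered it (1,500 data sets each). With near-continuous event dates the median was unchanged in 39%, 15% and 1.5% of data sets. With PD dated exactly on the scans those shares were 76%, 66% and 45%.

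**6. Informative discontinuation.** Let the hazard after discontinuation be kL, with p = 5% and median 6. Main: S(t) = exp(−(L+M)t) + ∫₀ᵗ M·exp(−(L+M)s)·exp(−kL(t−s)) ds. SAP rule: exp{−∫₀ᵗ L·exp(−(L+M)u)/S(u) du}. Censoring at discontinuation: exp(−Lt). At 12 months:

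| k | Main | SAP rule | Censor at discontinuation |
|---|---|---|---|
| 2 (worse afterwards) | 24.2% | 25.8% | 25.0% |
| 0.5 (better afterwards) | 25.8% | 26.6% | 25.0% |

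Censoring at discontinuation can land on either side of the main result; the SAP rule is above it both times.

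**The case against.** - *The departure from Table 6 is declared.* SAP 7.1 openly states an exception to 14.2.5, so this is not an internal contradiction. That stands. The fault is in what the exception does.
- *The curve has a definition.* Censoring one kind of event on its own date is how a cause-specific hazard is built, here for PD or death without prior COVID-19 discontinuation. That is true of the hazard. But one minus its product-limit curve is not a PFS probability in any population, and the SAP reports it as PFS.
- *The effect is small.* At n = 80 and 25% PFS the binomial standard error is √(0.25 × 0.75/80) = 4.8 points, a 95% half-width of about 9.5, against a shift of 0.5 to 2.7 points at a 6-month median. That limits the harm. The two analyses use the same participants, however, so the shift is a one-way artefact of the rule and not sampling noise.
- *Censoring at discontinuation is not neutral.* It rests on discontinuation being non-informative, and SAP 7.1 itself recognises infection as one route by which participants are affected. Step 6 shows the consequence, so the strategy should be named. Excluding discontinuers, as for best overall response, is no safer. It conditions on a later event: with complete follow-up, PFS among non-discontinuers has hazard L/(1−p), giving 12-month PFS of exp(−1.3863/0.95) = 23.2% at 5% and exp(−1.3863/0.90) = 21.4% at 10%, against a true 25.0%.
- *The data are open.* COVID-19 discontinuations are tabulated, and PFS event status is summarised and listed. A careful reader could spot the relabelled events, but the output would still be wrong.

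**Conclusion.** The concern holds. Both passages state the rule clearly, and its one-way effect follows from the estimator without any assumption. At or above is the exact statement: the curves coincide when no COVID-19 discontinuer has a later event. The size does rest on assumptions. With 5% to 10% discontinuing before their event, a median of 4 to 12 months and non-informative discontinuation, 12-month PFS is overstated by 0.6 to 3.1 points. The reach is one descriptive, IRC-based sensitivity output for a secondary endpoint in the combination arm. Main PFS and the primary ORR do not change. It should be corrected because the analysis cannot do the job it was added for.

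**What to change.** In SAP 7.1 and in the PFS row of the estimands table (SAP 14), replace the rule with: participants who discontinue study treatment due to COVID-19 before PD or death are censored at the last evaluable tumor assessment on or before the discontinuation date, or at the start of study treatment if there is none. This follows the convention of Table 6 in SAP 14.2.5. State in both places that this is a hypothetical strategy (PFS had COVID-19 discontinuation not occurred) and that it assumes non-informative discontinuation.

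The cost is wording in two places and one censoring-date derivation for this output. No new data are needed.

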8.1 Definition of Analysis Populations

Full Analysis Set (FAS) / Safety Analysis Population (SAF)

All participants who were administered any dose of any study treatment (regardless of the protocol version). Analyses will consider participants as treated and will be performed per treatment arm. As the definition of these analysis sets is identical, from now on the SAF Analysis Set will be referenced only.

Modified Full Analysis Set (mFAS)

The mFAS is defined as a subset of the FAS consisting of those participants who were tested MET amplification positive based on central TBx FISH testing (T+) or based on central LBx test (L+), or both, and who progressed on first-line osimertinib as the only prior line of therapy in the noncurative advanced or metastatic NSCLC setting (participants enrolled under any protocol version who meet the above criteria). The intent of introducing the mFAS is to enable easier entitling of respective efficacy tables and figures, there is no change of the analysis strategy as planned per study protocol.

For the fifth IDMC and for the primary analysis, participants from the Chinese extension period who started study treatment after the 8th July 2022 (i.e., date of completion of global enrollment) will be excluded from this analysis set due to insufficient length of follow-up, whereas they will be included in the mFAS for analysis of the Chinese extension period and for the final analysis.

Unless otherwise stated, all efficacy tables and figures will be based on the mFAS. The efficacy results for all the participants in the FAS will be listed.

Primary Analysis Set for Efficacy

The primary analysis set for efficacy will consist of all mFAS participants with advanced or metastatic EGFRm+ NSCLC and MET amplification, determined centrally by FISH (central TBx FISH testing [T+]). The primary analysis set for the combination treatment arm supports the primary objective of the study.

Secondary Analysis Sets for Efficacy

Two secondary analysis sets for efficacy will be defined:

- All mFAS participants with advanced or metastatic EGFRm+ NSCLC and MET amplification, determined centrally by LBx test (L+)
- All mFAS participants with advanced or metastatic EGFRm+ NSCLC and MET amplification, determined centrally by either TBx or LBx test (T+ and/or L+).

Safety Run-In Analysis Set (SRIAS)

The SRIAS will include all participants treated in the safety run-in who received at least 75% of the tepotinib and osimertinib planned dose and completed the DLT period (3 weeks after start of treatment with study treatment), or who experienced a DLT during the DLT period regardless of the received amount of each study treatment.

Planned tepotinib dose: $500 \text{ mg} \times 21 \text{ days} = 10500 \text{ mg}.$

Planned osimertinib dose: $80 \text{ mg} \times 21 \text{ days} = 1680 \text{ mg}.$

DLTs are identified as those AEs with answer "Yes" to the question "Is this adverse event a dose limiting toxicity", which is collected on the "Adverse Event Details" eCRF page. The respective eCRF flag will reflect the decisions of the SMC regarding the assessment of an adverse event being a DLT.

Pharmacokinetic Analysis Set (PKAS)

All participants who receive at least one dose of study treatment, have no important events or protocol deviations affecting PK and provide at least one measurable post-dose concentration.

The PKAS will include all participants:

• Who have PK data without any relevant protocol deviations and factors likely to affect the validity of these data

• With adequate study treatment compliance (i.e., dosing and dosing regimen is as scheduled on the PK measurement day(s), as well as on prior days which have the potential to impact PK results).

• With evaluable PK data, i.e., non-missing values sufficient to derive PK endpoints.

If participants received prohibited concomitant therapy or medicines, as specified in Section 6.5 of the protocol (refer to clinical study protocol MS200095-0031), they will be excluded from the PKAS. Relevant decisions will be made before database lock.

Additionally, the following will be considered for inclusion in the PKAS: if a participant has a tepotinib dose change, the affected PK data (for both tepotinib and osimertinib treatment) will no longer be included in the PKAS from the time of the change.

If there is a change in scheduled osimertinib dose which can affect osimertinib PK (e.g., inadequate washout of prior osimertinib treatment or missed osimertinib doses), the affected osimertinib concentrations and/or PK parameters will be excluded from the PKAS.

All PK summaries will be based on the PKAS population.

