6.5.3 Prohibited Medicines

Any additional concomitant therapy or procedure that becomes necessary during the study and any change to concomitant drugs must be recorded in the corresponding section of the eCRF, noting the name, dose, duration, and indication of each drug.

The following are not permitted during the study:

- Any other concomitant cancer drug therapy, including chemotherapy, biological therapy, hormonal therapy for anticancer purposes, targeted therapy, or any investigational product other than tepotinib and osimertinib as defined in this protocol
- Any concomitant medication known to prolong the QT interval and cause Torsade de Pointes (refer to [Appendix 8](#))
- Drug(s), for which the package insert/SmPC includes a contraindication for P-gp (eg, dabigatran, aliskiren, colchicine), BCRP, OCT1, OCT2, MATE1, MATE2, or OATP1B1 inhibiting drugs
- Drug(s) that are known to be potent inducers of CYP3A or P-gp and thereby may decrease efficacy of osimertinib and tepotinib, including carbamazepine, phenytoin, rifampicin, and Saint John's wort.

Use of prohibited medicines for any reason must result in withdrawal of the participant from this study. For further details with regard to drug-drug interactions, refer to the tepotinib IB.

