8.5 Pharmacokinetics

- The following PK parameters will be calculated, when appropriate:

Symbol	Definition
AUC _{0-t}	The area under the concentration-time curve (AUC) from time zero (= dosing time) to the last sampling time (t_{last}) at which the concentration is at or above the lower limit of quantification. Calculated using the mixed log-linear trapezoidal rule (linear up, log down).
$C_{L/f}$	The apparent total body clearance of study intervention following extravascular administration, taking into account the fraction of dose absorbed. $C_{L/f} = \text{Dose}_{p.o.} / \text{AUC}_{0-\infty}$. Either the observed or predicted $\text{AUC}_{0-\infty}$ should be used, depending on the study specific requirements.
C_{max}	Maximum observed concentration
t_{max}	The time to reach the maximum observed concentration collected during a dosing interval (unless otherwise defined, take the 1 st occurrence in case of multiple/identical C_{max} values)
$V_{z/F}$	The apparent volume of distribution during the terminal phase following extravascular administration, based on the fraction of dose absorbed. $V_{z/f} = \text{Dose} / (\text{AUC}_{0-\infty} * \lambda_z)$ following single dose. $V_{z/f} = \text{Dose} / (\text{AUC}_t * \lambda_z)$ following multiple dose.

- Whole blood samples of approximately 3 mL will be collected for measurement of plasma concentrations of tepotinib and metabolites, as specified in the Schedule of Activities. Samples for rich PK sampling (safety run-in only) will be obtained at Cycle 1 Day 1 and Cycle 1 Day 15 (at predose, 0.25, 0.5, 1, 1.5, 2, 3, 4, 6, 8, 12, and 24 hours after tepotinib administration). Samples for sparse PK sampling will be obtained at Cycle 1 Day 1 and Cycle 2 Day 1 (at predose, 1.5, and 4 hours after tepotinib administration). The actual date and time (24-hour clock time) of each sample will be recorded to calculate actual time elapsed since the prior dose administration.
- The quantification of tepotinib and metabolites in plasma will be performed using a validated method. Concentrations will be used to evaluate the PK of tepotinib.

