9.3 Populations for Analyses

The analysis populations are specified below. The final decision to exclude participants from any analysis population will be made during a data review meeting prior to database lock.

All participants who provided informed consent for Prescreening/Screening will be analyzed in terms of participant disposition only.

Analysis Set	Description
Full Analysis Set (FAS)/Safety Analysis Population (SAF)	All participants, who were administered any dose of any study intervention. Analyses will consider participants as treated and will be performed per treatment arm (and per dose level, in case multiple dose ranges were applied). Analyses of safety and efficacy will be based on this analysis set.
Primary Analysis Set for Efficacy (Primary FAS)	The primary analysis set for efficacy will consist of all FAS participants with advanced or metastatic EGFRm+ NSCLC and MET amplification, determined centrally by FISH. This analysis set supports the primary objective of the study.
Safety Run-In Analysis Set (SRIAS)	The SRIAS will include all participants treated in safety run-in who receive at least 75% of the tepotinib and osimertinib planned dose and complete the DLT period (3 weeks after start of treatment with study intervention), or who experience a DLT during the DLT period regardless of the received amount of each study intervention.
PK Analysis Set	All participants, who receive at least one dose of study intervention, have no clinically important protocol deviations or important events affecting PK, and provide at least one measurable post-dose concentration. The PK population will include all participants: Who have completed all study periods without any relevant protocol deviations and factors likely to affect the comparability of PK results. With adequate study intervention compliance With evaluable PK data, ie, non-missing values for primary endpoints in each study period. If participants received prohibited concomitant therapy or medicines, as specified in Section 6.5, they will be excluded from the PK population. Relevant decisions will be made before database lock. All PK analyses will be based on this analysis set.

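### As written, the PK analysis set drops a whole participant for any prohibited medicine, with no time window and no PK-relevance condition, so a medicine first taken after the last PK sample removes earlier concentrations it cannot have affected from the PK summaries

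*SAP*

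**What the plan says.** The PKAS definition in SAP 8.1 contains a sentence on prohibited medicines. It opens "If participants received prohibited concomitant therapy or medicines, as specified in Section 6.5 of the protocol" and, after a cross-reference, ends "they will be excluded from the PKAS. Relevant decisions will be made before database lock". Protocol 9.3 has the parent rule: "If participants received prohibited concomitant therapy or medicines, as specified in Section 6.5, they will be excluded from the PK population". In both places the unit removed is the participant. Neither sentence mentions when the medicine was taken or whether it can influence tepotinib or osimertinib concentrations.

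The list it points to, Protocol 6.5.3, has four classes: other anticancer therapy; QT/Torsade drugs ("Any concomitant medication known to prolong the QT interval and cause Torsade de Pointes"); drugs contraindicated with inhibitors of P-gp, BCRP and other transporters; and potent CYP3A or P-gp inducers. Only the inducers are given a reason tied to reduced effect of the study drugs.

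Two neighbouring rules in SAP 8.1 are narrower. The opening PKAS criterion admits participants who "have no important events or protocol deviations affecting PK". When the tepotinib dose is altered, the SAP says: "the affected PK data (for both tepotinib and osimertinib treatment) will no longer be included in the PKAS from the time of the change". The osimertinib dose-change rule is likewise confined to the affected osimertinib data.

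On timing, Protocol 8.5 states: "Samples for sparse PK sampling will be obtained at Cycle 1 Day 1 and Cycle 2 Day 1". Rich sampling in the safety run-in is on Cycle 1 Days 1 and 15, so its last 24-hour sample falls on Day 16. SAP 8.1 bases every PK summary on the PKAS.

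**The concern.** A concentration measured on Day 16 or Day 22 cannot be altered by a medicine first taken months later. Under the written rule that medicine nevertheless takes the participant's whole PK record out of the summaries. Whether early PK data count then depends on events after sampling, and so on how long the participant stays on treatment. A PK analysis set should not have that property.

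What is at stake is the descriptive part of the secondary PK objective. It matters most for the run-in group with rich profiles, which Protocol 2.3 collects to look at each drug's exposure when given with the other. That group is small enough for one avoidable exclusion to show in the precision of the geometric means, for which SAP Section 9 plans 95% CIs.

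**Working it through.** The documents give no figure to reproduce here, so the check is a comparison of the rules followed by two illustrations.

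**1. The exclusion rules side by side (SAP 8.1)**

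| Trigger | What is removed | Limited to PK relevance? | Limited in time? |
|---|---|---|---|
| Deviations and events in general | participant | yes | no |
| Tepotinib dose change | affected data for both drugs | yes | yes, from the change onward |
| Osimertinib dose change affecting its PK | affected osimertinib data | yes | in effect, through the word affected |
| Prohibited medicine | participant | no | no |

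The last row is the only one with neither limit. The nearest boundary in time is indirect: SAP Section 12 defines concomitant medication by the on-treatment periods, which Table 3 ends at last dose + 30 days, data cut-off or death.

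**2. How much of the exposure window lies after sampling**

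Inputs: last rich sample Day 16; last sparse visit Cycle 2 Day 1, about Day 22 with 21-day cycles (Day 25 at the end of the ±3-day window); 1 month = 30.4375 days (SAP 9.6). Treatment duration is not given, so 3 to 12 months is assumed.

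Share of treatment time after the last sample = 1 − last sampling day / treatment days.

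- 3 months (91.3 days): sparse 1 − 22/91.3 = 76%; rich 1 − 16/91.3 = 82%
- 6 months (182.6 days): sparse 88%; rich 91%
- 9 months (273.9 days): sparse 92%; rich 94%
- 12 months (365.25 days): sparse 94%; rich 96%

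Using Day 25 for the sparse visit lowers its range only to 73%–93%. So for these durations most of the time in which a prohibited medicine could trigger exclusion comes after the PK data are complete. This describes the window. It does not say how often such medicines are used.

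**3. Cost of losing a rich-PK participant**

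Input: 6 participants evaluated in the run-in, with none added afterwards (Protocol 4.3). For a mean on the log scale, the 95% CI half-width is SD × t(0.975, n − 1)/√n. With the SD held fixed, the factor is:

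- n = 6: 1.049
- n = 5: 1.242, ratio 1.242/1.049 = 1.18, about 18% wider
- n = 4: 1.591, ratio 1.591/1.049 = 1.52, about 52% wider

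**The case against.** The strongest reply is that exclusion is not automatic. Both documents leave decisions to a point before database lock, Protocol 9.3 refers final exclusions to a data review meeting, and SAP 6.3 and 6.5 have such a meeting agree the analysis sets. The general PKAS criterion would give that meeting a reason to keep a participant whose medicine came after sampling. This stands in part: the written rule may not be the one finally applied. But no criterion is stated for overriding a sentence that says participants will be excluded. Read strictly, the rule over-excludes; read loosely, it leaves an unspecified choice in an open-label study.

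A second reply is that Protocol 6.5.3 already requires withdrawal from the study after prohibited use. That governs conduct from then on and says nothing about samples already taken. Protocol 7.2 lets data collected up to a withdrawal of consent be used.

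The remaining replies limit the point, and they stand.

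- A reader might infer that the data are lost. They are not: SAP 16.1.1 and 16.1.2 flag excluded data with the reason and list PK parameters for every participant with enough data. Population PK has its own plan.
- A reader might infer that QT-listed drugs are irrelevant to PK and should never lead to exclusion. The documents do not establish this. A QT reason for barring a drug does not show that it has no PK effect, and Protocol 2.3 describes tepotinib as a P-gp substrate whose exposure could rise under inhibition. For use before or during sampling, a cautious exclusion is defensible.
- A reader might infer selective bias, since nausea and vomiting are recognised reactions to tepotinib and ondansetron is in Protocol Table 6. Nothing in the documents links use of these drugs to tepotinib exposure, so neither direction nor size of bias can be shown.
- A chance of losing one of the six could be computed only from an assumed rate of use. The documents give none, and QT-prolonging co-medication is also an entry exclusion.

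**Conclusion.** The point holds in this form: the prohibited-medicine sentence is broader than its purpose and inconsistent with the rules beside it. Followed literally, it drops concentrations that a later medicine cannot have influenced. It is a stated rule that gives a worse result, not a missing detail, and it is worth correcting.

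Its reach is small. Only descriptive PK summaries are affected, and no formal PK hypotheses are planned. The 18% and 52% figures apply only if 1 or 2 of the 6 rich-PK participants are actually excluded, and they assume an unchanged SD. The timing shares assume treatment of 3 to 12 months.

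It would be wrong to conclude that the dose decision is in doubt. The Safety Monitoring Committee worked from participant profiles and confirmed the RP2D in August 2020, independently of the PKAS. Efficacy and safety populations do not use this rule.

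**What to change.** Replace the sentence in SAP 8.1 with:

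> PK records collected on or after the start of a prohibited medicine judged able to affect tepotinib or osimertinib PK (judged at data review without reference to the participant's concentrations) are excluded from the PKAS from that time; prohibited medicines started after the participant's last PK sample do not lead to exclusion.

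Because Protocol 9.3 carries the same rule, declare the departure in SAP Section 7, which already records changes to the planned PK parameters. The list of prohibited medicines does not change.

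The cost is this wording, the Section 7 entry, and a check of medication start dates against PK sampling dates at data review. The small downside is a case-by-case judgement of PK relevance for medicines taken before or during sampling. Making that judgement without sight of the participant's concentrations keeps it from depending on the results.
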